#### 6.4.2. Additional considerations

Following analyses will be performed:

- *As part of safety endpoint assessment:*
  - *The percentage of subjects with at least one local (solicited and unsolicited) AE, with at least one general (solicited and unsolicited) AE and with any (solicited and unsolicited) AEs during the solicited 7-day follow-up period will be tabulated with exact 95% CI after each vaccine dose and overall (1-Additional Dose and Revaccination groups). The same tabulation will be performed for grade 3 solicited adverse events;*
- *Duration of each separate solicited local and general AE during the solicited follow-up period will be presented. Total duration of each individual (any and grade 3) solicited local and general AE will be tabulated. Tabulations will be provided on duration of solicited symptoms ongoing beyond the 7-day (Days 0-6) post vaccination period*
- *Number and percentage of subjects with fatal SAEs, classified by MedDRA Primary System Organ Class and Preferred Term will be presented with exact 95% CI in two ways:-*
  - *With respect to onset of fatal SAE:- With onset of fatal SAE within 30 days post each vaccination for 1-Additional Dose and Revaccination group and within 30 days post Month 0 and Month 2 visit for Control group; with onset of fatal SAE within 12 months post last vaccination for 1-Additional Dose and Revaccination group and within 12 months post Month 0 visit for Control group; with onset of fatal SAE from study start up to study end for all groups collected in Expedited AE report as per protocol.*
  - *With respect to date of death:- Who died within 30 days post each vaccination for 1-Additional Dose and Revaccination group and within 30 days post Month 0 and Month 2 visit for Control group; with death within 12 months post last vaccination for 1-Additional Dose and Revaccination group and within 12 months post Month 0 visit for Control group; with death from study start to study end for all groups collected in Expedited AE report as per protocol.*

*Please note – before protocol amendment 2, the fatal SAEs were collected in the Expedited AE report and after protocol amendment 2 only the related fatal SAE were reported in Expedited AE report.*

- *Listing of subjects who died (related and not related to vaccination before Protocol Amendment 2) and their fatal SAEs collected in Expedited AE report.*
- *Listing of subjects who died (not related to vaccination) collected in the study continuation form after protocol amendment 2.*
- *Listing of intercurrent medical condition for all groups*
- *As per recommendation from CBER, following 2 tables will be generated for 1-Additional dose and Revaccination group:*

- subjects with Grade 3 non-serious unsolicited AEs up to 30 days post each vaccination (day 0-29)
- subjects with Grade 3 non-serious unsolicited AEs with causal relationship to vaccination up to 30 days post each vaccination (day 0-29)
- *As per recommendation from CBER, the following analysis will be performed by age strata 2, gender, race, ethnicity and region:-*
  - *Percentage of SAEs reported related to investigational vaccine, related to study participation or concurrent GSK medication/vaccine, during the entire study period for the LTFU group.*

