### **9.3. Detecting and recording adverse events, serious adverse events and pregnancies**

#### **9.3.1. Time period for detecting and recording adverse events, serious adverse events and pregnancies**

The time period for collecting and recording SAEs will begin at the first study visit Month 0 and will end at the last study visit/ contact at the end of the study for each subject. See Section [9.4](#) for instructions on reporting of SAEs.

SAEs that are related to the investigational vaccine will be collected and recorded from the time of the first receipt of study vaccine until the subject is discharged from the study.

All AEs/SAEs leading to withdrawal from the study will be collected and recorded from the time of the first study visit Month 0 up to the last study visit/ contact at the end of the study\*.

\* If the AEs/SAEs leading to withdrawal from the study are not related to investigational vaccine, study participation or to GSK concomitant medication/vaccine, or if not due to HZ complications, only the name (diagnosis/description) of the event will be recorded in the eCRF. No other details about these type of AEs/SAEs will be recorded during the entire study (for the LTFU group), after 12 months from visit Month 0 (for the Control and 1-Additional Dose groups) and after 12 months from last HZ/su vaccination (for the Revaccination group).

**CONFIDENTIAL**201190 (ZOSTER-049 EXT:006-022)  
Protocol Amendment 5 Final

In addition to the above-mentioned reporting requirements and in order to fulfil international reporting obligations, SAEs that are related to study participation (i.e., protocol-mandated procedures, invasive tests, a change from existing therapy) or are related to a concurrent GSK medication/vaccine will be collected and recorded from the time the subject consents to participate in the study until she/he is discharged from the study.

An overview of the protocol-required reporting periods for AEs/SAEs, IMCs and HZ complications for the LTFU group is given in [Table 25](#). An overview of the protocol-required reporting periods for AEs/SAEs, IMCs and HZ complications as well as medically attended events and pIMDs for the 1-Additional Dose, Revaccination and Control groups, and pregnancies for the 1-Additional Dose and Revaccination groups as applicable, is given in [Table 26](#).

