**If the follow-up period to be considered is from the primary study ZOSTER-006/022 study**

- *at the day after first vaccination (Month 0) if analyses are done on the Total Vaccinated Cohort for efficacy, or*
- *at 30 days after second vaccination (Month 3) if analyses are done on the mTVC or ATP cohort for efficacy.*

The follow-up time for each subject **will end:**

- at the time of the event; or,
- *at the time of receiving any vaccination for shingles which is not assigned as per protocol (for mTVC only); or,*
- at the latest visit for which data is available for subjects in case of no event. Practically, this will be set at the minimum date between the following dates
  - Date of withdrawal
  - Date of death *collected on the conclusion page for the subject who died*
  - Date of study conclusion
  - Cut off date for interim reporting for Y2, Y4

Start date of confirmed HZ case will be the earliest of the start date of the rash or start date of the pain to assess the onset of HZ, whichever comes first.

***Consideration on subjects who had HZ/PHN/HZ related complication (other than PHN) cases in ZOSTER-006/022 studies and were enrolled into ZOSTER-049 study:***

- *For the VE analysis in the prevention of HZ/PHN/HZ related complication (other than PHN) over the total duration of the ZOSTER-049 study, these subjects with previous confirmed cases will be excluded from ZOSTER-049 data.*

- *For the VE analysis in the prevention of HZ/PHN/HZ related complication (other than PHN) from one month post dose 2 in the ZOSTER-006/022 studies until the end of the ZOSTER-049 study, the first confirmed case will be considered, and the corresponding follow-up times will be censored to the time at 1st confirmed episode.*

*As there is no elimination code in primary studies ZOSTER-006/022 which eliminate subject with confirmed HZ episode, it will not be identified by elimination but rather by creating flag based on the w\_algo dataset generated during primary analysis.* The follow-up time will be calculated in days as Date of end of follow-up period – Date of vaccination +1 and expressed in person-years at risk (number of days/365.25).

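### The whole-study fatal-SAE and death percentages in SAP 6.4.2 rest on a source whose capture rule changes with time and group, so they measure neither all-cause nor related mortality

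*SAP*

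**What the plan says.** SAP 6.4.2 states: "Number and percentage of subjects with fatal SAEs, classified by MedDRA Primary System Organ Class and Preferred Term will be presented with exact 95% CI". It does this twice, once by onset of the fatal SAE and once by date of death. Each version has a 30-day window and a 12-month window for the randomised groups, and a whole-study window for all groups. The whole-study windows read "with onset of fatal SAE from study start up to study end for all groups collected in Expedited AE report as per protocol" and "with death from study start to study end for all groups collected in Expedited AE report as per protocol".

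A note directly below says that fatal SAEs went into the Expedited AE report before Protocol Amendment 2, and that "after protocol amendment 2 only the related fatal SAE were reported in Expedited AE report". The remaining deaths have a separate output: "Listing of subjects who died (not related to vaccination) collected in the study continuation form after protocol amendment 2". No percentage is attached to that listing.

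Protocol 9.3.1 sets the recording rule for events leading to withdrawal that are neither related nor due to HZ complications: only the name of the event is entered. For LTFU, "No other details about these type of AEs/SAEs will be recorded during the entire study (for the LTFU group"). For the randomised groups the rule starts later: "after 12 months from visit Month 0 (for the Control and 1-Additional Dose groups"), and 12 months after the last vaccination for Revaccination. Table 26, footnote b, keeps reporting of all SAEs open for the same windows. Related means related to the investigational vaccine, to study participation or to a GSK concomitant product.

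**The concern.** A percentage with an exact interval needs one event definition applied to everyone in the denominator. Here the definition depends on when the death occurred and on which group the subject was in. A reader of a table of subjects who died between study start and study end, with a percentage and a 95% CI, will take it for mortality. In a study of older adults followed for about six years, that reading could be far too low. The opposite reading, that the table shows related deaths only, also fails, because unrelated deaths from the early period are included.

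The consequence is confined to safety reporting. The efficacy analyses take the date of death from another source and are not affected.

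**Working it through.** The documents state no death count, death rate or precision for these tables, so there is no planned figure to reproduce. The check has two parts.

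**1. What reaches the whole-study tables**

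| Group | Unrelated deaths captured | Unrelated deaths not captured |
|---|---|---|
| LTFU (at most 14,208 of 14,448 subjects, protocol Table 1) | Those before Amendment 2 | All those after it |
| Control, 1-Additional Dose | Those within 12 months of Month 0 (all-SAE window) | Those after the window, once Amendment 2 applies |
| Revaccination | Those from Month 0 to 12 months after the last dose | Those after the window, once Amendment 2 applies |

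Related fatal SAEs are captured throughout in every group.

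A subject whose death is not captured remains in the denominator:

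- SAP 5.1 defines the safety population for LTFU and Control as everyone who came to Month 0. For the two vaccinated groups it is everyone dosed in this study.
- Protocol 11.6.1 treats a subject with no reported SAE as having no event.

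Such a death is therefore scored as a non-event. The numerator mixes all-cause and related deaths, and the direction of error against all-cause mortality is always downwards.

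**2. Illustration of size (assumptions, not trial data)**

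Inputs:

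- Amendment 2 is dated 19 January 2017 (protocol Appendix C). Its effective date at each site is not given and may be later.
- The SAP 6.3.3 worked example uses Month 0 dates of 2 February 2016 and 5 July 2016. These lie 352 days (352/365.25 = 0.96 years) and 198 days (0.54 years) before the amendment.
- Follow-up T is 6 years. For Revaccination, visits are timed from Month 2 (protocol Table 10), so T = 74 months, with 14 months of all-SAE reporting.
- The all-cause hazard m is **assumed** constant at 0.5% to 4% a year. Related deaths are taken as about zero.

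Share of all-cause deaths captured = (1 − exp(−m·t)) / (1 − exp(−m·T)), where t is the time under all-fatal-SAE reporting.

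| Subject | t | m = 0.5% | m = 2% | m = 4% |
|---|---|---|---|---|
| LTFU, enrolled after Amendment 2 | 0 | 0% | 0% | 0% |
| LTFU, 0.54 years before | 0.54 y | 9.2% | 9.5% | 10.1% |
| LTFU, 0.96 years before | 0.96 y | 16.3% | 16.9% | 17.7% |
| Control, 1-Additional Dose | 12 months | 16.9% | 17.5% | 18.4% |
| Revaccination | 14 of 74 months | 19.2% | 19.9% | 20.9% |

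In absolute terms at m = 2%, six-year mortality would be 1 − exp(−0.12) = 11.3%. For LTFU subjects enrolled 0.54 or 0.96 years before the amendment, the table would show 1.1% (1 − exp(−0.02 × 0.54)) or 1.9% (1 − exp(−0.02 × 0.96)). For those enrolled after it, the table would show about 0%.

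The captured share hardly moves with the assumed hazard. It is driven by t/T, which differs by group and by enrolment date.

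**The case against.** **The strongest defence** is that the SAP is open about all this. It qualifies both whole-study items by their source, states the change directly below them and does not call the result a death rate. The analyses are descriptive, all-cause mortality is not a stated primary or secondary endpoint, and no between-group comparison of deaths is planned. SAP 6.4.1 already tabulates related SAEs to study end in all groups, which is a constant definition containing the related fatal ones. Together, the planned listings would let a reader count all deaths by hand.

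Most of that is fair, and it limits the weight of the point. It does not rescue the two percentages. Naming the source does not give the interval a definable target, and a by-hand count from listings does not replace a correct table.

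**Stronger readings that the documents do not support:**

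- *After Amendment 2 only vaccine-related deaths count in every group.* The SAP note taken alone invites this. Protocol 9.3.1 and Table 26 keep all-SAE reporting for 12 months in the randomised groups, and related is wider than vaccine-related. HZ complications are also exempt from name-only recording.
- *The 30-day and 12-month tables are compromised too.* Under the current protocol they fall inside the all-SAE window. They would be in doubt only if the SAP note described actual practice in those groups, which is why the two texts need reconciling.
- *Deaths were not collected.* They were. The fault lies in the tabulation.
- *A particular fraction of deaths is missed.* Any such figure rests on assumed mortality and enrolment timing.

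**Conclusion.** The concern holds for the two study-start-to-study-end tables, in all four groups, but for different reasons. In LTFU the capture rule changed at Amendment 2. In Control, 1-Additional Dose and Revaccination, all-SAE reporting is assured only for the 12-month window. In both cases later unrelated deaths are scored as non-events, so the percentages understate all-cause deaths and their exact intervals estimate neither all-cause nor related mortality.

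The direction is certain, provided any unrelated death falls outside the captured period. The size is not derivable from the documents. Under the stated assumptions, about 79% or more of deaths would be absent in every group, and nearly all for LTFU subjects enrolled after the amendment. This should be corrected before the end-of-study outputs. It does not touch the efficacy results or the short-window safety tables.

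**What to change.** Replace the two whole-study percentages in SAP 6.4.2 with:

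1. **All-cause deaths by group.** Merge the Expedited AE report with the study continuation/conclusion form, one record per subject. Show n, % and the rate per person-year, ending follow-up at death, withdrawal or last contact. Person-years are needed because protocol 10.2.1 means information stops at withdrawal, so a crude six-year percentage would count withdrawn subjects as alive.
2. **Related fatal SAEs by SOC and PT for the whole study**, presented as a subset of the related-SAE table already planned in SAP 6.4.1, using the protocol's definition of related.

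Keep the 30-day and 12-month tables for the randomised groups. Amend the SAP 6.4.2 note so that it agrees with protocol 9.3.1 and Table 26 on the 12-month all-SAE window. Use one name for the non-expedited source: 6.4.2 calls it the continuation form, while SAP 7.3.1 takes the date of death "collected on the conclusion page for the subject who died".

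The cost is a wording change and one merged dataset. The deaths are already collected for the listing, and the date of death is already used to end efficacy follow-up. No new data collection is needed.

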## **7. STATISTICAL CALCULATIONS**

### **7.1. Derived and transformed data**

#### **7.1.1. Date derivation**

- SAS date derived from a character date: If day is missing, 15 is used. If day and month are missing, 30 June is used.
- Onset day for an event (ae, medication, vaccination, ...): The onset day is the number of days between the last study vaccination and the onset/start date of the event. This is 0 for an event starting on the same day as a vaccination. See SAS date derived in case the start date of the event is incomplete.
- Duration: The duration of an event is expressed in days. It is the number of days between the start and the stop dates + 1. Therefore, duration is 1 day for an event starting and ending on the same day.

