#### **5.4. According to Protocol Cohort for immunogenicity – (1-Additional Dose, Revaccination and Control groups)**

The ATP cohort for immunogenicity will include all subjects from the TVC:

- Who meet all eligibility criteria;
- Who have received 1 dose (1-Additional Dose group) or 2 doses (Revaccination group) of study vaccine(s) according to their random assignment;
- For whom administration site of study vaccine is known and correct;
- Who have not received a vaccine not specified or forbidden in the protocol;
- Who complied with the procedures defined in the protocol;
- Who did not receive a medication/ product leading to exclusion from an ATP analysis;
- Who did not present with an IMC leading to exclusion from an ATP analysis;
- Who complied with the vaccination schedule, i.e., 49-83 days between the first and the second dose for the Revaccination group;
- Who complied with the Month 1 blood sample schedule, i.e., 28-48 days from Month 0 to Month 1 for the 1-Additional Dose group and Control group;
- Who complied with the post-Dose 2 blood sample schedule, i.e., 28-48 days post-Dose 2 for the Revaccination group;
- Who had immunogenicity results available post-dose 1 for the 1-Additional Dose group, post dose 2 for the Revaccination group and at Month 1 and Month 3 for the Control group;
- Who had no episode of HZ prior to study start;
- Who received 2 doses of HZ/su vaccine in the primary ZOSTER-006/022 studies.

*Please note – To avoid long title for the OPS based on this cohort, the cohort name to be used in the OPS is ‘ATP cohort for humoral immunogenicity – Randomized groups’ and ATP cohort for CMI immunogenicity – Randomized groups’ for humoral and CMI analysis, respectively.*

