### 6.4. **Analysis of safety**

#### 6.4.1. **Analysis of safety planned in the protocol**

The analysis will be performed on the TVC.

The results for the analysis of safety will be tabulated as follows:

- The percentage of subjects with at least one local solicited AE, with at least one general solicited AE and with any solicited AEs during the solicited 7-day follow-up period will be tabulated with exact 95% CI after each vaccine dose and overall (1- Additional Dose and Revaccination groups). The same tabulation will be performed for grade 3 solicited adverse events;
- The percentage of subjects reporting each individual solicited local and general AE during the solicited 7-day follow-up period will be tabulated with exact 95% CI (1- Additional Dose and Revaccination groups). For all solicited symptoms, the same tabulation will be performed for grade 3 solicited AEs, grade 3 related, **medically attended** and for solicited general AEs with **causal** relationship to vaccination (1- Additional Dose and Revaccination groups);

- The percentage of subjects reporting temperature by half degree (°C) cumulative increments. Similar tabulations will be performed for any fever with a causal relationship to vaccination and for any fever resulting in a medically attended visit (1-Additional Dose and Revaccination groups);
- The percentage of subjects with at least one report of unsolicited AE classified by the MedDRA Preferred Terms and reported up to 30 days after each vaccination will be tabulated with exact 95% CI (1-Additional Dose and Revaccination groups). *The same tabulation will be performed for grade 3 unsolicited AEs, for unsolicited AEs with a relationship to vaccination and grade 3 unsolicited AEs related to vaccination;*
- The percentage of unsolicited AEs resulting in a medically attended visit will also be tabulated (*Control, 1-Additional Dose and Revaccination groups. The table for medically attended unsolicited adverse events will be presented within 30 days post each vaccination for 1-Additional Dose and Revaccination group and within 30 days post Month 0 and Month 2 visit for Control group. The medically attended unsolicited adverse events will also be presented from first vaccination up to 6 months post last vaccination for 1-Additional Dose and Revaccination group and within 6 months of Month 0 visit for Control group.*

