#### **7.1.2. Dose number**

- The study dose number is defined in reference to the number of study visits at which vaccination occurred. More specifically dose 1 refers to all vaccines administered at the first vaccination visit while dose 2 corresponds to all vaccinations administered at the second vaccination visit even if this is the first time a product is administered to the subject.
- Relative dose: the relative dose for an event (AE, medication, vaccination) is the most recent study dose given before an event. In case the event takes place on the day a study dose is given, the relative dose will be that of the study dose, even if the event actually took place before vaccination. For instance, if an adverse event begins on the day of the study vaccination but prior to administration of the vaccine, it will be assigned to this dose. In case a study dose is not administered, and an event occurs after the subsequent study dose (e.g., 2nd study dose), the relative dose of the event will be study dose associated to the subsequent study dose (e.g., dose 2).
- The number of doses for a product is the number of times the product was administered to a subject.
- The incidence per dose is the number of vaccination visits at which an event was reported among all vaccination visits.

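### The SAP's partial-date rule takes no account of the dose date, so a post-dose adverse event with a missing day can be dated before the dose and leave its 30-day window

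*SAP*

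**What the plan says.** SAP 7.1.1 gives one rule for every character date: "If day is missing, 15 is used. If day and month are missing, 30 June is used". It defines onset day as follows: "The onset day is the number of days between the last study vaccination and the onset/start date of the event". It then refers incomplete event dates back to the rule: "See SAS date derived in case the start date of the event is incomplete".

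SAP 7.1.2 defines dose attribution: "the relative dose for an event (AE, medication, vaccination) is the most recent study dose given before an event". Its only timing allowance is for an event on the calendar day of a dose, which goes to that dose even if it began before the injection.

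The windows that depend on these derivations are in SAP 6.4. Unsolicited AEs in the two vaccinated groups are those "reported up to 30 days after each vaccination will be tabulated with exact 95% CI (1-Additional Dose and Revaccination groups"). Section 6.4.2 adds tables of "subjects with Grade 3 non-serious unsolicited AEs up to 30 days post each vaccination (day 0-29"). SAEs, pIMDs, medically attended unsolicited AEs and fatal SAEs also have 30-day tables. For these the Control group is included, with windows anchored to the Month 0 and Month 2 visits. SAEs and pIMDs are also tabulated from first vaccination to 12 months after the last dose.

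SAP 7.6 and protocol 11.6.1, which deal with missing data, add no date rule that would override 7.1.1.

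**The concern.** A missing day is usual enough that the SAP has a rule for it, but the rule can contradict what the site knows. If a subject is vaccinated on 20 March and later reports an event that began in March after the injection, the only dates consistent with the report are 20 to 31 March. The SAP assigns 15 March.

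Such an event is no longer a post-dose event in the analysis. The SAP counts all vaccinated subjects in the denominators for unsolicited AEs and SAEs (7.5.1), so the subject still counts in N but the event does not appear in the window. With 60 subjects per vaccinated group, one event is 1/60 = 1.7%. The per-dose rates after one or two additional doses are what these tables are meant to show. The result also sits oddly with SAP 7.1.2, which resolves same-day uncertainty in favour of counting the event.

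**Working it through.** The plan states no figure on this point, so there is none to reproduce. The check applies the rule as written.

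**Inputs.** Imputation rule and onset-day definition: SAP 7.1.1. Dose attribution: SAP 7.1.2. Window, days 0 to 29: SAP 6.4.2. Interval between doses in the Revaccination group, 49 to 83 days: SAP 5.4. Planned doses: 60 × 1 + 60 × 2 = 180. Assumptions, not from the documents: dose dates uniform over 1 January 2016 to 31 December 2019 (1,461 dates), true onset uniform over days 0 to 29, giving 1,461 × 30 = 43,830 combinations.

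**Formula.** Derived onset day = imputed date − dose date. The event is kept if the result is 0 to 29.

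**When it goes wrong.** With only the day missing, a same-month event is dated before the dose whenever the dose was given on the 16th or later. That is 365 − 12 × 15 = 185 of 365 calendar days, 50.7%.

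**Dose 1 example.** Dose on 20 March, event on 25 March (true day 5), recorded as March. Imputed 15 March, onset day 15 − 20 = −5. No earlier dose in this study exists to receive it.

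**Dose 2 example.** Dose 2 on 20 May, event on 25 May, recorded as May. Imputed 15 May, 5 days before dose 2. Counted from dose 1, the onset day is the gap minus 5: 44, 55 or 78 for gaps of 49, 60 or 83 days.

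**Dose 2 in general.** The imputed date precedes dose 2 by 1 day (dose on the 16th) to 16 days (dose on the 31st). The dose-1 onset day therefore runs from 49 − 16 = 33 to 83 − 1 = 82. It never falls in dose 1's 0 to 29 window, so the event is in neither window.

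**Share dated before the dose, day missing.** A dose on day d ≥ 16 of a month with M days has M − d + 1 same-month onset days. Summed over d this gives 136 for a 31-day month, 120 for a 30-day month, 91 for a 28-day February and 105 for a 29-day February. A common year gives 7 × 136 + 4 × 120 + 91 = 1,523 and a leap year 1,537. Four years give 3 × 1,523 + 1,537 = 6,106, and 6,106/43,830 = 13.9%.

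**Full enumeration.**

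| Missing part | Dated before dose | Dated after Day 29 | Kept in window |
|---|---|---|---|
| Day | 13.9% | 11.5% | 74.6% |
| Day and month | 46.4% | 45.4% | 8.2% |

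For true onset on days 0 to 6 with the day missing, 40.9% are dated before the dose. In the other direction, 11.5% of events that began 1 to 30 days before a dose are pulled into the window.

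**With a floor at the dose date**, tested for a single dose: with the day missing, events dated before the dose fall from 13.9% to 0% and those kept rise from 74.6% to 88.5%. With day and month missing, 46.4% falls to 0% and 8.2% rises to 54.6%. The floor does not recover events pushed past Day 29.

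All percentages are conditional on the date being partial.

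**The case against.** The best case against is that partial onset dates will be rare. Unsolicited events are recorded on a 30-day diary card (protocol 6.3.1.2 and Table 6) and reviewed with the subject at Month 1 or Month 3 (protocol 6.5.10). SAEs and pIMDs are reported within 24 hours (protocol Table 28), and SAP 7.6 promises queries on missing recordings. The analysis is descriptive. This stands and limits the size of the point; a year-only onset for a diary-card event is hardly plausible.

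It can also be said that 7.1.2 does not state that the imputed date drives dose attribution, and that the table specifications are in a separate document. That is fair, but it changes little. An event kept with dose 2 has a negative onset day, and one moved to dose 1 falls on day 33 to 82. Neither is in a Day 0-29 window.

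Four stronger readings are tempting and are not supported:

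- *SAE, pIMD and fatal-SAE counts are lowered throughout.* A dose-2 SAE or pIMD moved before dose 2 stays in the 12-month table. All SAEs and pIMDs in the expedited reports are listed, related SAEs are tabulated to study end, and fatal SAEs are also tabulated to study end and by date of death (SAP 6.4.1, 6.4.2).
- *The error runs one way and biases the group comparison.* Pre-dose events can also be pulled in, and Control events in the shared tables follow the same date rule.
- *SAP 7.6.4 turns these subjects into non-events.* That sentence concerns subjects who did not report, not reported events that are misdated.
- *Half of the events are lost.* The 51% is the share of calendar days on which a dose is exposed. The corresponding share of day-missing events is 13.9%.

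**Conclusion.** The point holds as a minor defect in the SAP. A stated rule gives a date that is impossible for an event known to follow the dose, and nothing elsewhere in the SAP or protocol corrects it. The loss is clearest for non-serious unsolicited AEs in the 30-day tables, and for any dose-1 event in the tables that run from first vaccination. For SAEs and pIMDs after dose 2 it is confined to the 30-day tables.

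The size in practice cannot be computed, because the number of partial onset dates is not given. With about 180 planned doses and diary-card collection, a few events is a reasonable expectation. The percentages rest on evenly spread dose dates and onset days. The defect does not threaten the study's conclusions, but it is cheap to remove.

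**What to change.** Add to SAP 7.1.1, for start dates of AEs, SAEs, pIMDs and medically attended events in all three randomised groups:

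- If the known month and year match those of a study dose (for Control, the Month 0 visit or the Month 2 visit/contact), and the event was not recorded as present beforehand, use the later of the standard imputed date and that dose or visit date. With doses 49 to 83 days apart, both doses cannot fall in one month, so the match is unambiguous.
- If only the year is known, use the later of 30 June and the first dose or visit date in that year, under the same condition. Using the most recent dose instead would draw more events from months later into the 30-day window.
- Flag imputed onsets in the listings.

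Control must be included because it shares the SAE, pIMD, fatal-SAE and medically attended tables; a floor for the vaccinated groups alone would treat the randomised groups differently.

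The cost is a short SAP addition and a small derivation change. A few events of truly unknown timing may be counted as post-dose; for instance, a year-only event in a subject first dosed after 30 June would be placed on the dose day. Events pushed past Day 29 remain unrepaired. The Month 3 results were planned for inclusion in the Year 2 report (SAP 8.1), so end-of-study tables may differ slightly from that output, and a footnote should say so.
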